18.1 SUBSTUDY PURPOSE

We propose the addition of baseline, three month, and three year gated SPECT exercise myocardial perfusion imaging as additional study endpoints. The design of the trial is amenable

to the performance of substudies on this population, however this substudy will likely require external sources of funding due to current NIH funding constraints.

18.2 PRIMARY ENDPOINT

- To examine the chronic effect of study drug on changes in perfusion defect size (ischemic burden) from baseline to three year perfusion stress test.

18.3 SECONDARY ENDPOINTS

- To examine the acute effect of study drug on coronary vasomotor tone. This will be done by comparing the degree of ischemic burden between the baseline study and three month nuclear stress test.
- To correlate baseline exercise perfusion study with initial patient symptoms and angiographic findings.
- To determine if initially positive perfusion scans predict subsequent patient symptoms, and clinically important outcomes. To determine the ability of the initial exercise perfusion study to select a subset of patients who receive greater benefits from study drugs in terms of angiographic progression, ischemic burden, symptoms, and cardiac event rates.
- To study the effects of hormone replacement therapy on the ECG changes during standard treadmill exercise testing.
- To examine the acute and chronic effects of study drug on exercise capacity, and to correlate this with patient reported functional status as measured by standardized questionnaires.

18.4 SUBSTUDY PROTOCOL

- All women randomized to participation in the overall trial will be asked to participate in this substudy.
- Women will undergo exercise gated SPECT imaging within 7 days of randomization and prior to initiation of study drug. The exercise protocol will include use of a standard Bruce

protocol with gated SPECT myocardial perfusion imaging. Technetium 99 tomography will be performed at rest and following exercise with reinjection performed in patients with fixed defects.

- At three months, during one of their follow up visits, women will undergo repeat exercise treadmill test. For those women who had perfusion defects initially, a follow up gated SPECT perfusion image will also be obtained at this time point. Those women with negative perfusion scans at enrollment will undergo only exercise ECG testing at the three month time point.
- At completion of the protocol and prior to 3 year recatheterization, all women will undergo repeat Bruce treadmill testing and gated SPECT perfusion imaging. (see Figure 1)

18.5 METHODS

- Treadmill ST segment changes during and immediately following exercise will be analyzed by readers without prior knowledge of patient treatment or clinical history in a treadmill core lab.
- All perfusion imaging will be read and analyzed in a blinded fashion by a nuclear core lab. Gated SPECT was selected for its improved ability to differentiate soft tissue attenuation and to integrate data on resting ventricular function. Data image analysis will include attenuation correction software. Images will be scored both qualitatively and semi-quantitatively. The use of Technetium 99, with a single stress injection, permits simultaneous accurate measurement of LVEF and wall motion through the acquisition of first pass data, and of perfusion from subsequent SPECT imaging. These LVEF and wall motion data have been shown to add incremental information for the diagnosis of significant coronary disease as well as incremental prognostic information over SPECT imaging alone.

18.6 DATA ANALYSIS

The goal of this analysis is to examine the acute and chronic effects of hormone replacement therapy and antioxidants on direct vascular tone, ischemia, and treadmill variables using stress myocardial perfusion and function imaging. Each woman's perfusion defect size will be quantified as a percentage of the total area on a bulls eye plot on enrollment, three month, and three year gated SPECT perfusion studies. We can quantify the changes in magnitude of ischemic burden by treatment group using a simple linear regression model. We hypothesize that some will improve, some will worsen and some will show no change. If our evaluation of the data reveals a large group without change, we will consider a categorical analysis of the data. Additionally, we will control for interim non-protocol drug therapy. Comparing the enrollment study to the three year study will look at the ability of study drug to change ischemic burden by affecting atherosclerotic progression which is the primary endpoint of the substudy. Comparing the enrollment study to the three month study will look at direct effects of study drug on vascular tone and responsiveness.

New ECG changes in the absence of perfusion changes at the three month test will be analyzed by treatment group to examine the potential effects of drug therapy alone on ECG parameters. The initial stress perfusion image will also be compared with patient symptoms, and with angiographic findings at enrollment. The degree to which minor luminal narrowings can cause ischemic burden through functional or dynamic stenoses will be examined. Additionally, we will determine if abnormal perfusion scans at enrollment are predictive of future symptoms, angiographic findings, and outcomes. We will look at the ability of perfusion imaging to identify those women who benefit most from treatment in terms of ischemic burden, symptoms, and outcome.

Functional status and exercise duration may be affected by hormone replacement therapy. Enrollment treadmill tests will be compared to the those obtained at the three month and three year endpoint to look at the acute and chronic effects of drug therapy on exercise capacity. We will compare Bruce treadmill variables and estimated metabolic equivalents to responses on functional status questionnaires regarding activity levels in everyday life. Changes in functional status will be compared across treatment groups.

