18.7 STATISTICAL POWER

The primary endpoint (change in ischemic burden) can be as a continuous or a dichotomous endpoint. The advantage of the continuous endpoint is that it requires a smaller sample size to reach statistical significance. The disadvantage with this approach, however, is the inability to easily account for those patients who require revascularization or die prior to repeat perfusion imaging. For example, a patient who develops ischemia at two years and receives bypass surgery may have a normal three year perfusion image. One method for handling patients undergoing interval revascularization would be to attempt a repeat perfusion image prior to revascularization. If this is not clinically feasible, we could assign a standardized perfusion deduction based upon the number of diseased vessels revascularized.

Alternatively, one could use a dichotomous approach, defining a successful therapy as one which prevented both the progression of ischemic territory or the occurrence of clinical endpoints (e.g., MI, CV death, revascularization) by three years. For initial sample size calculations, we have estimated 15-35% of our population would reach one of these endpoints. Sample size calculations with this dichotomous endpoint are displayed below.

Table 1. Treatment Effect Needed To Reach Significance Based on Event Rate

Event Rate Placebo Arm	Event Rate Treatment Arm	RR	Power*
15%	6.5%	2.3	80%
20%	10%	2.0	80%
25%	14%	1.8	80%
30%	18%	1.7	80%
35%	22.5%	1.6	80%

*Assumes a sample size of 225 patients per arm.

Table 2. Patients Needed or Study Power Assuming a 1.30 RR Treatment Effect

Event Rate Placebo Arm	RR	Study Power*	Fixing Power	Sample Size Required**
15%	1.3	20%	80%	1160
20%	1.3	25%	80%	955
25%	1.3	30%	80%	781
30%	1.3	35%	80%	651
35%	1.3	41%	80%	548

* Assuming a sample size of 225.

** Assuming a power of 80%.

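### The only model named for the continuous SPECT endpoint leaves out baseline defect size, which costs precision but does not bias the comparison on average

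*Protocol*

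**What the plan says.** Appendix E of the Protocol (section 18) describes the SPECT substudy. Section 18.2 gives its primary aim: "To examine the chronic effect of study drug on changes in perfusion defect size (ischemic burden) from baseline to three year perfusion stress test".

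Section 18.4 plans a scan for every participant before treatment starts: "Women will undergo exercise gated SPECT imaging within 7 days of randomization and prior to initiation of study drug". Section 18.6 says how the scan becomes a number: "Each woman's perfusion defect size will be quantified as a percentage of the total area on a bulls eye plot". This is done at enrollment, three months and three years.

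For the analysis, section 18.6 states: "We can quantify the changes in magnitude of ischemic burden by treatment group using a simple linear regression model". One adjustment follows: "Additionally, we will control for interim non-protocol drug therapy". Baseline defect size is not named as a covariate anywhere in Appendix E.

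The plan is not firmly closed. Section 18.6 allows for a categorical analysis if many women show no change, and section 18.7 says: "The primary endpoint (change in ischemic burden) can be as a continuous or a dichotomous endpoint". The power tables in 18.7 cover only the dichotomous version.

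**The concern.** Change in defect size is tied to where a woman starts. Defect size cannot fall below zero, so a woman with a normal entry scan can only stay the same or get worse, while a woman with a defect can also improve. The protocol expects both kinds, since section 18.4 schedules three-month imaging only for women whose entry scan showed a defect. Those women are selected on a raised first value, so some regression toward the mean is likely in that comparison too.

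A model of change on treatment group leaves this predictable variation in the error term. The one covariate named is measured after randomisation, while the pre-treatment measurement of the same quantity goes unused. At stake is the precision of the substudy's primary comparison. Section 18.7 prefers the continuous endpoint because it needs fewer patients, and the named model gives part of that advantage away.

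**Working it through.** **The plan's own figure.** There is none to reproduce. The documents give no SD, effect size, correlation or power for the continuous endpoint.

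**Inputs.**
- Sample size: 225 per arm (section 18.7, stated for the dichotomous tables).
- Alpha: two-sided 0.05 (section 10.4, stated for the main trial and assumed for the substudy).
- rho, the correlation between baseline and three-year defect size: assumed, 0.3 to 0.9.
- Change-score power of 0.80: assumed, as a reference point only.

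**Variance.** With the same SD s at both scans:
- change score: 2s²(1-rho)
- adjusted for baseline: s²(1-rho²)
- ratio: (1-rho²)/[2(1-rho)] = (1+rho)/2

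**Power.** Power of 0.80 corresponds to a noncentrality of 1.960 + 0.842 = 2.802. Adjusted power is the normal probability below 2.802/√ratio - 1.960. At rho 0.5: 2.802/√0.75 = 3.235, and 3.235 - 1.960 = 1.275, giving 0.899.

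**Chance imbalance.** For a given baseline difference between arms, the change-score estimate moves by -(1-rho) times that difference. One standard error of the baseline difference at 225 per arm is √(2/225) = 0.094 SD. The standard error of the change-score contrast is 0.094 × √[2(1-rho)], so the shift is √[(1-rho)/2] of that standard error.

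| rho | variance ratio | adjusted n per arm matching 225 unadjusted | adjusted power (change score 0.80) | shift for a 1-SE imbalance (SD) | shift as share of the contrast's SE |
|---|---|---|---|---|---|
| 0.3 | 0.65 | 147 | 0.935 | 0.066 | 0.59 |
| 0.5 | 0.75 | 169 | 0.899 | 0.047 | 0.50 |
| 0.7 | 0.85 | 192 | 0.860 | 0.028 | 0.39 |
| 0.8 | 0.90 | 203 | 0.840 | 0.019 | 0.32 |
| 0.9 | 0.95 | 214 | 0.820 | 0.009 | 0.22 |

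**Simulation check** (normal data, equal variances, 225 per arm, 4,000 trials per rho):

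| rho | variance ratio | power, change v adjusted | mean estimate, change v adjusted | true effect |
|---|---|---|---|---|
| 0.5 | 0.750 | 0.79 v 0.89 | 0.261 v 0.261 | 0.264 |
| 0.7 | 0.855 | 0.80 v 0.85 | 0.204 v 0.204 | 0.205 |
| 0.9 | 0.957 | 0.81 v 0.83 | 0.118 v 0.118 | 0.118 |

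The precision loss appears as the algebra predicts. Both estimators centre close to the true effect, as they should, because the baseline imbalance has mean zero under randomisation.

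**Unequal variances.** Let s0 and s1 be the SDs at baseline and three years, and k = s1/s0. The change-score variance minus the adjusted variance is s0² - 2·rho·s0·s1 + rho²·s1² = (s0 - rho·s1)², which is never negative. The ratio becomes k²(1-rho²)/(1 + k² - 2·rho·k):
- rho 0.7, k 1.25: 0.797/0.8125 = 0.98
- rho 0.8, k 1.25: 0.5625/0.5625 = 1.00, no gain

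The gain vanishes at rho·k = 1, and adjustment does not become the less precise choice. The imbalance shift, -(1 - rho·k) times the difference, vanishes at the same point.

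**The case against.** The strongest case against has four parts.

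- **Detail for an analysis plan.** A covariate list for an ancillary study is often left to a separate plan, and nothing in Appendix E forbids baseline adjustment. This stands in part: such a plan may already include baseline. But section 18.6 is not silent. It names a model and a covariate, and what it names omits the obvious predictor.
- **The analysis is not settled.** The wording is permissive, the endpoint may be dichotomous, and a categorical analysis may be chosen after the data are seen. The extra covariate also shows that the model is not strictly single-predictor. This stands, and the point therefore applies only if the continuous endpoint is used. A reader might infer that the protocol commits to an unadjusted comparison of changes. It does not go that far.
- **Bias.** A reader might infer that leaving out baseline biases the result. Under randomisation it does not. What remains is the shift conditional on the imbalance that happens to occur, which is the precision loss seen from another side and not a second defect.
- **Size.** Rho and the starting power are assumptions. The floor at zero, with many normal scans, makes equal-variance normal theory only approximate. Section 18.7's suggested standard deduction for revascularised women could widen the follow-up spread. All of this stands and makes the size uncertain. It does not reverse the direction.

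Baseline adjustment also leaves two matters in 18.6 and 18.7 untouched: how deaths and revascularisations enter the continuous endpoint, and whether a post-randomisation covariate belongs in the model.

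**Conclusion.** The point holds as a limited one. If the continuous endpoint is used, the only model named in section 18.6 omits baseline percent defect size and so discards precision that the planned data would supply. Under equal variances the loss is equivalent to between 35% of the sample (rho 0.3) and 5% (rho 0.9). From an assumed 0.80, power would rise by about 14 points at one end and 2 at the other. A larger follow-up variance can reduce the gain to zero. No single figure should be quoted as the expected gain, because the documents do not give the correlation or the variances.

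The matter is minor. Section 7.2 lets women decline the substudy, section 18.1 expects it to need outside funding, and the main trial's endpoint, rank test and sample size do not depend on it.

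**What to change.** In section 18.6, state that when the continuous endpoint is used, three-year defect size (or change from baseline) is regressed on the HRT and antioxidant indicators with baseline percent defect size as a covariate. State the same model for three months, in the women scanned then. The randomisation strata from section 7.3, clinical center and hysterectomy status, may be added as factors, but no gain from them has been quantified here.

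The cost is one sentence in Appendix E. The baseline scan and the strata are already planned data, so no further scans or patients are needed.

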7.2 SCREENING VISIT

The study will be described to the potential participant and if she agrees to participate, an informed consent form should be reviewed and signed.

If creatinine and fasting triglycerides have been assessed within the past twelve months, no blood collection is necessary at this visit. If they are not available, the patient will be asked to fast for at least twelve hours prior to coming to clinic and a blood sample will be taken. This should be sent to the local laboratory for analysis of creatinine, triglycerides, FSH and INR, as necessary.

A general physical (including a mammogram, if none has been done in the last 12 months, a PAP smear and a pelvic examination) is to be completed. If a mammogram has been done within the past twelve months, the coordinator will obtain a medical release from the patient and obtain a copy of the results. For women participating in the Brachial Artery Reactivity Study (see appendix D) and the Effects of Hormone Replacement Therapy on Electrocardiographic and Scintigraphic Measures of Myocardial Ischemia Study (see appendix E) appropriate assessments will be performed. However, a woman who is otherwise eligible may refuse either or both of these studies and still be randomized into the WAVE trial.

Comment [TBC1]:

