10.4 SAMPLE SIZE CALCULATIONS

The sample size calculations are based on a change in mean MLD using a t-test. The antioxidant and HRT components are treated as separate trials (no interaction is assumed). No adjustment for multiple comparisons will be made.

The type 1 error rate α was 0.05 (2-tailed). Although a rank test will be used, given the sample sizes contemplated in the study, the power of the rank test is essentially the same as that of the t-test under the assumption of normality. The power calculations are based on the effect size, defined as the expected difference in outcome between treatment and control divided by the

standard deviation of the outcome (the outcome here is the change in mean MLD between baseline and follow-up). The effect sizes for four published studies are summarized below.

STARS	FATS	SCRIP	MARS
0.86	0.51	0.29	0.14

The weighted average of these effect sizes, weighing by the number of patients in each study is 0.334. With this effect size and a power of 0.90, the required total sample size is N=380. Assuming a dropout rate of 15%, 450 patients are needed. If a 20% dropout rate is assumed, the power of the test for various effect sizes is summarized in the table below:

	N=450	N=425	N=400	N=375	N=350
ES=0.30	0.81	0.79	0.77	0.74	0.71
ES=0.35	0.91	0.90	0.88	0.86	0.83
ES=0.40	0.97	0.96	0.95	0.93	0.92

Based on these considerations, 400 patients is considered the minimum acceptable sample size for the study. The target sample size for the study is 450 patients.

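### Appendix E adjusts its treatment comparison for drug therapy started after randomization, and, separately, its power and sample-size figures are not what the design delivers

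*Protocol*

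**What the plan says.** Section 18.6 sets out the analysis of the continuous endpoint, change in perfusion defect size: "We can quantify the changes in magnitude of ischemic burden by treatment group using a simple linear regression model". A categorical analysis is to be considered if many women show no change. The next sentence reads: "Additionally, we will control for interim non-protocol drug therapy". It is not called a sensitivity analysis, and no comparison without the covariate is named as primary.

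Section 18.7 leaves open whether the primary endpoint is continuous or dichotomous, and gives power for the dichotomous version only. Table 1 lists pairs of event rates with 80% power, with the footnote "Assumes a sample size of 225 patients per arm". Table 2 is headed "Patients Needed or Study Power Assuming a 1.30 RR Treatment Effect" and gives required sizes of 1160, 955, 781, 651 and 548 for placebo rates of 15, 20, 25, 30 and 35%, with powers of 20, 25, 30, 35 and 41% at a sample size of 225. Neither column of Table 2 is labelled per arm.

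Elsewhere, section 10.4 sets the trial's target at 450 women and works with dropout of 15% and 20%. Section 7.2 makes the substudy optional: "a woman who is otherwise eligible may refuse either or both of these studies and still be randomized into the WAVE trial".

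**The concern.** The two defects are separate. The covariate belongs to the continuous regression, and the power tables concern the dichotomous endpoint.

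On the covariate: drugs started during follow-up can be a consequence of the assigned treatment. Conditioning on them can remove part of the treatment effect. It can also introduce imbalance in whatever prompted the prescription, so the comparison loses the protection of randomization. If this is the only model reported, a reader cannot recover the randomized comparison.

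On the power figures: Table 1 needs every randomized woman to take part and be evaluable, which sections 7.2 and 10.4 do not lead one to expect. Table 2 is the basis on which a reader would judge what size of substudy could detect a relative risk of 1.30, and its first rows understate that size.

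**Working it through.** **The covariate.** No arithmetic applies, because the protocol gives no figure for interim drug use. The protocol does supply both links in the path.
- Study drug to interim drugs: section 2.3.1 says estrogen alters HDL, LDL and triglycerides, and sections 18.3 and 18.8 expect possible effects on symptoms and ischemia. All of these can prompt lipid-lowering or antianginal prescribing.
- Interim drugs to endpoint: section 18.8 cites a 30% decrease in ischemic territory with short-term fluvastatin.

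Interim therapy can therefore lie between treatment and outcome. The main trial's primary analysis (section 10.2.2) is by intention to treat; section 18.6 names no equivalent.

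**Power: inputs.** Placebo rates, treatment rates (Table 1), relative risk 1.30 as placebo over treatment (Table 2; same direction as Table 1, where 20% against 10% is 2.0), 80% power and 225 per arm are from section 18.7. Two-sided alpha 0.05 is assumed from section 10.4, since Appendix E gives none.

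**Formulas** (p̄ is the mean of p₁ and p₂)
- n = [1.960·√(2p̄(1−p̄)) + 0.8416·√(p₁(1−p₁)+p₂(1−p₂))]² / (p₁−p₂)²
- With continuity correction: n_c = (n/4)·[1+√(1+4/(n·|p₁−p₂|))]²
- Power at N per arm = Φ{[|p₁−p₂| − 1/N − 1.960·√(2p̄(1−p̄)/N)] / √([p₁(1−p₁)+p₂(1−p₂)]/N)}; drop 1/N for the uncorrected version.

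**Reproducing the protocol's figures.** Table 1 at 225 per arm, corrected, gives 79.0, 81.3, 80.9, 82.1 and 80.9%, so its 80% is sound at that size (83-85% uncorrected). Table 2 reproduces closely only per arm, with continuity correction and whole-percent treatment rates of 11, 15, 19, 23 and 27%:
- required n: 1158, 945, 781, 652, 549 (stated 1160, 955, 781, 651, 548)
- power at 225 per arm: 20.0, 24.5, 29.5, 35.0, 41.0% (stated 20, 25, 30, 35, 41%)

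Those rates are relative risks of 1.36, 1.33, 1.32, 1.30 and 1.30.

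**Table 2 at exactly 1.30.** First row: p₂ = 0.15/1.3 = 0.1154, difference 0.0346, p̄ = 0.1327. n = (0.9403 + 0.4033)²/0.0346² ≈ 1507 with unrounded values; corrected, 1564. All rows, corrected (uncorrected in brackets):

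| Placebo rate | Treatment rate | Stated n | n per arm needed | Stated n is | Power at stated n | Power at 225: stated | Power at 225: recomputed |
|---|---|---|---|---|---|---|---|
| 15% | 11.54% | 1160 | 1564 (1507) | 25.8% short (23.0% short) | 0.67 (0.69) | 20% | 15.4% (19.0%) |
| 20% | 15.38% | 955 | 1115 (1072) | 14.3% short (10.9% short) | 0.73 (0.75) | 25% | 21.1% (24.9%) |
| 25% | 19.23% | 781 | 846 (812) | 7.7% short (3.8% short) | 0.77 (0.78) | 30% | 27.4% (31.3%) |
| 30% | 23.08% | 651 | 666 (638) | 2.3% short (2.0% over) | 0.79 (0.81) | 35% | 34.3% (38.3%) |
| 35% | 26.92% | 548 | 538 (514) | 1.9% over (6.6% over) | 0.81 (0.83) | 41% | 41.7% (45.7%) |

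**Table 1 with fewer evaluable women.** Range over its five rows. The protocol gives no participation rate, so values below 100% are assumptions.

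| Participation | Dropout | N per arm | Corrected | Uncorrected |
|---|---|---|---|---|
| 100% | 15% | 191 | 71-75% | 77-79% |
| 100% | 20% | 180 | 68-72% | 74-76% |
| 80% | 15% | 153 | 60-64% | 67-69% |
| 60% | 15% | 115 | 46-51% | 55-57% |

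**The case against.** **The adjustment is not shown to bias anything.** Section 5 masks women and staff partly so that concomitant treatment stays similar between arms. A reader might infer that the substudy's estimate is biased by design. The protocol does not support that: bias arises only if treatment changes interim drug use, and no size or direction is given. Masking does not remove the possibility, though. A masked physician still responds to lipids and symptoms, and section 5 concedes that side effects may suggest an assignment. So the adjustment can bias the comparison, and that is as far as the point goes.

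**The Table 2 error is concentrated and changes no decision.** This stands. The 26% shortfall is one row, the last two rows are about right, and these sizes set no enrolment. Table 2 already discloses only 20-41% power at 225; recomputed, it is 15-42% corrected. The heading nevertheless says 1.30, and the 15% row was evidently computed at 1.36.

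**Table 1 declares its assumption.** It does, and its arithmetic is right. Uncorrected, there is some slack (83-85% at 225), but the correction is the method that reproduces Table 2. Deaths and revascularizations count as events in the dichotomous endpoint, so its missing-data rate may differ from the main trial's dropout. This is a reason to state the expected evaluable number.

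**Appendix E is a proposal.** Section 18.1 says it will probably need outside funding, and the trial's primary analysis does not depend on it. That limits the importance but does not make the statements correct.

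**The three-month ECG analysis.** Section 18.6 plans that "New ECG changes in the absence of perfusion changes at the three month test will be analyzed by treatment group", while section 18.4 says "Those women with negative perfusion scans at enrollment will undergo only exercise ECG testing at the three month time point". A reader might infer an analysis that cannot be done. The schedule simply confines it to women imaged at both times, so it is at most a clarification.

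**Conclusion.** Two independent, modest defects in Appendix E.

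1. The only treatment model described for the continuous endpoint is to be controlled for a post-randomization variable, with no comparison free of it named as primary. This can bias the result; size and direction are unknown.

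2. The power figures for the dichotomous endpoint are optimistic. With 15-20% dropout and no refusals, Table 1's power is about 68-75% corrected (74-79% uncorrected) instead of 80%; refusals lower it further by an amount the protocol does not allow one to fix. Table 2's required sizes are 26%, 14%, 8% and 2% short in the first four rows and slightly conservative in the fifth.

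These figures assume two-sided 0.05 and the main trial's dropout carried over to the substudy. The stronger inference, that faulty sample sizes make the comparison biased or that Table 2 is wrong throughout, does not follow: sample-size arithmetic does not bias an estimate, and the upper-rate rows are close.

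**What to change.** - **Section 18.6:** name as primary the intention-to-treat comparison without interim drug therapy, adjusted for baseline covariates only, if any. Describe interim drug use by arm. Keep any drug-adjusted model as a labelled sensitivity analysis.
- **Section 18.7, Table 2:** recompute at exactly 1.30 with unrounded treatment rates, label both the sizes and the 225 as per arm, and state alpha, sidedness and the use of a continuity correction.
- **Section 18.7, Table 1:** restate power for the expected evaluable number, over a range of participation and dropout.

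The cost is appendix wording and less favourable power figures. No scans are added and the main trial is unaffected.
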